6.3 Exploratory objectives

Commercially Confidential Information

Commercially Confidential Information

Commercially Confidential Information

7 Statistical methods for safety and tolerability data

All subjects within the safety analysis set will be included in the safety data analysis.

7.1 Variables

Adverse events, vital signs (blood pressure, pulse rate, body temperature), ECG intervals, clinical laboratory measurements, immunogenicity, hematology, blood chemistry as well as subject demographics, baseline characteristics, and treatment information, with primary of interest the systemic and local Adverse Events, ECGs, vital signs, hematology, blood chemistry and urinalysis.

7.2 Descriptive analyses

All safety variables will be summarized descriptively by treatment group for Part A and Part B, separately.

Subject demographics and other baseline characteristics

All data for background and demographic variables will be listed by treatment group and subject. Summary statistics will be provided by treatment group.

Relevant medical history, current medical conditions, results of laboratory screens, drug tests and any other relevant information will be listed by treatment group and subject.

Treatment

Data for study drug administration (rescue medication) and concomitant therapies will be listed by treatment group and subject.

Vital signs

All vital signs data will be listed by treatment, subject, and visit/time and if ranges are available abnormalities (and relevant orthostatic changes) will be flagged. Summary statistics will be provided by treatment and visit/time.

ECG evaluations

All ECG data will be listed by treatment group, subject and visit/time, abnormalities will be flagged. Summary statistics will be provided by treatment and visit/time.

Clinical laboratory evaluations

All laboratory data will be listed by treatment group, subject, and visit/time and if normal ranges are available abnormalities will be flagged. A separate listing is provided presenting all parameters in a subject with any abnormal values. Summary statistics will be provided by treatment and visit/time.

Adverse events

All information obtained on adverse events will be displayed by treatment and subject.

The number and percentage of subjects with adverse events will be tabulated by body system and preferred term with a breakdown by treatment. A subject with multiple adverse events within a body system is only counted once towards the total of this body system.

The number (and proportion) of subjects with AEs of special Interest (AESI) will be summarized by treatment.

The treatment emergent adverse events (TEAEs) are also included i.e. the adverse events started at or after the date of first administration of study treatment to 30 days after the date of the last administration of study treatment.

Immunogenicity

All immunogenicity results will be listed by treatment, subject and visit/time.

Commercially Confidential Information

9 Considerations due to COVID-19

Due to the COVID-19 pandemic, it was not possible to perform some procedures as per protocol. All deviations due to COVID-19 will be listed separately to other deviations and may be also tabulated.

Observations that were impacted due to COVID-19, may be excluded from the primary analyses and separately explored to identify if there is an impact of them on the analyses.

10 Reference list

Commercially Confidential Information

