11.1 **Analysis sets**

For all analysis sets, subjects will be analyzed according to the study treatment(s) received.

The safety analysis set will include all subjects that received any study drug.

The PK analysis set will include all subjects with at least one available valid (i.e. not flagged for exclusion) PK concentration measurement, who received LNA043 and with no protocol deviations that impact on PK data.

The primary pharmacodynamic (PD) analysis set will include all subjects with available PD data. The secondary PD analysis set will include all subjects with available PD data and no protocol deviations with relevant impact on PD data. Details of which protocol deviations have impact on PD data will be provided in the Statistical Analysis Plan (SAP).

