11.4.2 Statistical model, hypothesis, and method of analysis

The primary efficacy variables will be analyzed using the secondary PD analysis set and the primary safety variables using the safety analysis set.

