1.4.2 Part B

Approximately 75 patients will be enrolled in Part B and randomized. This is a non- confirmatory, randomized, placebo-controlled, patient and investigator blinded study in patients with Kellgren & Lawrence (K&L) with grade 2 or 3 with osteoarthritis (OA). At least 69 patients are expected to complete the study (10% drop out rate). Additional patients may be enrolled if the dropout rate will exceed 10%. Participants will be treated at four treatment visits.

Patients will be assigned to one of the following “three (3)” treatment arms in a ratio of “1:1:1, A:B:C”.

Study treatments are defined as:

A: single i.a. injection of 20 mg (4mL) LNA043, every 4 weeks	CCI
B: single i.a. injection of 40 mg (4mL) LNA043, every 4 weeks	CCI
C: single i.a. injection of placebo (4mL) every 4 weeks	CCI

Commercially Confidential Information

Commercially Confidential Information

2 First interpretable results (FIR)

Commercially Confidential Information

3 Interim analyses

Commercially Confidential Information

4 Statistical methods: Analysis sets

For subjects for which the actual treatment received does not match the randomized treatment the treatment actually received will be used for the analysis.

The safety analysis set will include all subjects that received any study drug.

The PK analysis set will include all subjects with at least one available valid (i.e. not flagged for exclusion) PK concentration measurement, who received any study drug and experienced no protocol deviations with relevant impact on PK data.

The pharmacodynamic (PD) analysis set will include all subjects with available PD data and no protocol deviations with relevant impact on PD data.

The analysis sets and protocol deviation codes are related as follows:

Table 4-1: Protocol deviation codes and analysis sets for Part A and Part B

Category Deviation code	Text description of deviation	Data exclusion
Subjects are excluded from PK analysis in case of these PDs:		
INCL01	Deviation from inclusion criterion 1	Yes
TRT01	Study treatment deviation, i.e. subject did not receive any study treatment or did not complete the full treatment (Part A) Major study treatment deviation i.e. subject did not receive the same dose throughout the study (Part B)	Yes
Subjects are excluded from PD analysis in case of these PDs:		
INCL01	Deviation from inclusion criterion 1	Yes

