TRT01	Study treatment deviation, i.e. subject did not receive any study treatment or did not complete the full treatment (Part A) Major study treatment deviation i.e. subject did not receive the same dose throughout the study (Part B)	Yes

If updates to this table are needed, an amendment to the SAP needs to be implemented prior to DBL.

Additional analyses may be considered in relation to the quality and interpretability of the MRI assessments for cartilage volume and thickness. Flags (ANL0XFLs) based on the comments related to insufficient image quality (e.g., “low”) will be derived in order to define these sets. The derivation logic for these will be described in the Programming Data Specifications (PDS).

5 Statistical methods for Pharmacokinetic (PK) parameters

All subjects within the PK analysis set will be included in the PK data analysis.

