5.1 Descriptive analyses

Due to a limited PK sampling, only summary statistics of measured PK concentrations will be reported, and no further PK parameters will be determined for this study.

LNA043 and ANGPTL3 serum and synovial fluid concentration data will be listed by subject, and visit/sampling time point, separately for each study part. Descriptive summary statistics will be provided by treatment, study part and visit/sampling time point, including

Commercially Confidential Information

Summary statistics will include mean (arithmetic and geometric), Standard Deviation (SD), CV (arithmetic and geometric), median, minimum and maximum.

The PK analysis will be done separately for part A and part B.

6 Statistical methods for Pharmacodynamic (PD) parameters

All subjects within the PD analysis set will be included in the efficacy PD data analysis, unless otherwise stated. For MRI related assessments, all subjects within the PD analysis set and subjects who completed Week 28 and/or Week 52, for Part B will be included.

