6.1.3.2 Part B

The primary efficacy variable for Part B, change from baseline in cartilage volume in the index region will be analyzed using a mixed effect model for repeated measures (MMRM) analysis of variance model, including all-time points to compare treatment groups at Weeks 28 and 52. The model will include baseline as a covariate, treatment, timepoint, treatment*timepoint as fixed effects. An unstructured covariance will be assumed; if not possible, other appropriate covariance structures will be explored such as Autoregressive (AR(1)), Compound symmetry, etc.

The change from baseline in cartilage thickness in the index region will be similarly analyzed using the MMRM described above for the change from baseline in cartilage volume in the index region.

A two-sided 90% confidence intervals for the treatment effect will be formed at Weeks 28 and 52. Considering that the time course of response to LNA043 is not known, statistically significant differences (one-sided p-value of treatment superiority to placebo at 95% significance level) between active drug (either LNA043 dose) and placebo at either Week 28 or Week 52 will be considered as a positive result. No multiplicity adjustment will be considered. If deemed appropriate, the endpoint measure data will be transformed to facilitate analysis.

Same analyses (table and figures) for the MMRM models of change from baseline in cartilage volume in the index region as well as for the change from baseline in the cartilage thickness in the index region may be implemented based on the Population A, defined in Section 6.

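### Does the optional exclusion of COVID-19-impacted observations in SAP Section 9 leave the primary analysis undefined?

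*SAP*

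**What the plan says.** Protocol 11.4.2 fixes the population for primary efficacy: "The primary efficacy variables will be analyzed using the secondary PD analysis set". Protocol 11.1 defines that set by the absence of deviations that matter for PD data, and leaves it to the SAP to say which deviations those are.

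SAP Section 4 takes this up: "The pharmacodynamic (PD) analysis set will include all subjects with available PD data and no protocol deviations with relevant impact on PD data". Table 4-1 then names two codes that remove a subject from PD analysis, INCL01 and TRT01, and adds a control: "If updates to this table are needed, an amendment to the SAP needs to be implemented prior to DBL". For the MRI endpoints, SAP Section 6 includes "all subjects within the PD analysis set and subjects who completed Week 28 and/or Week 52, for Part B will be included".

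SAP Section 9 adds two statements on the pandemic. The first concerns reporting: "All deviations due to COVID-19 will be listed separately to other deviations and may be also tabulated". The second is the permissive one: "Observations that were impacted due to COVID-19, may be excluded from the primary analyses". That sentence goes on to provide for exploring the impacted observations separately, to see whether they affect the analyses. It names neither study part and no endpoint.

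For Part B, SAP 6.1.3.2 calls the trial positive on a significant difference "between active drug (either LNA043 dose) and placebo at either Week 28 or Week 52 will be considered as a positive result", at one-sided 5% and with no multiplicity adjustment.

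**The concern.** The primary efficacy set depends on which deviations count, and Section 9 appears to open a second route for removing data outside Table 4-1. It works on observations, whereas the table works on subjects, so it is unclear whether the table's amendment rule covers it. Two analysts could both follow the SAP and fit the Part B model to different data.

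With 69 planned completers, or 23 per arm, a handful of scans could change whether a dose is called better than placebo. Protocol 11.5 does not impute MRI data, so an excluded scan simply leaves the model. Table 6-2 of the protocol allows statisticians and programmers to be unblinded at patient level from randomization onward, so the text does not guarantee that the choice is made without sight of treatment codes. At stake would be a result labelled positive that depended on an unstated choice.

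**Working it through.** **What is already fixed.** Three provisions narrow the opening.

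- Table 4-1 carries out the Protocol 11.1 commitment at subject level. Section 9 does not contradict it; it concerns single observations.
- Protocol 10.3 has protocol deviations determined before the database is locked and the codes released for analysis. COVID-19 deviations are among them and are listed separately, so the candidate observations can be identified by then.
- SAP Section 6 includes every PD-set subject unless otherwise stated. The natural default is therefore to include, with exclusion as a documented exception.

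Still open are the mapping from deviation to observation and the choice of headline version.

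**Inputs.** From the documents: 69 completers at 1:1:1 give 69/3 = 23 per arm; one-sided alpha 0.05; two visits; unstructured covariance (SAP 6.1.3.2). Assumed, because the documents give no figure: affected share p of 5%, 10% or 20%, independent of arm, outcome and visit; correlation r between visits of 0.5 or 0.8. The Part B effect size and SD are redacted.

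**Cost of excluding, one visit at a time.** 90% CI half-width = t(0.95, 3k−3) × √(2/k), in SD units, with k = 23(1−p):

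| p | k | half-width |
|---|---|---|
| 0 | 23 | 1.668 × 0.295 = 0.492 |
| 5% | 21.85 | 1.670 × 0.303 = 0.505 |
| 10% | 20.7 | 1.671 × 0.311 = 0.519 |
| 20% | 18.4 | 1.675 × 0.330 = 0.552 |

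At 20% the interval is 0.552/0.492 = 1.12 times as wide. This overstates the cost, because the planned model also uses the patient's other visit.

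**Cost under the planned model.** Treat the covariance as known and leave out the baseline covariate. Per-patient information on the two visit means is (1−p)² Σ⁻¹ + p(1−p) I, where Σ has unit variances and correlation r, and I is the identity matrix. At p = 0.20 and r = 0.8, 1/(1−0.64) = 2.778:

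- diagonal: 0.64 × 2.778 + 0.16 = 1.938
- off-diagonal: −0.64 × 0.8 × 2.778 = −1.422
- variance relative to complete data: 1.938/(1.938² − 1.422²) = 1.119
- standard error ratio: √1.119 = 1.058

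The same steps give these increases in standard error:

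| p | r = 0.5 | r = 0.8 |
|---|---|---|
| 5% | 2.0% | 1.0% |
| 10% | 4.2% | 2.3% |
| 20% | 9.5% | 5.8% |

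**Error rate.** For one comparison, the test statistics with and without the affected observations have correlation √(1−p) under the null. Each version alone rejects at 5%. The chance that at least one exceeds 1.645 is 5.9%, 6.3% and 6.9% for p = 5%, 10% and 20%. Simulation of the three-arm design, with a t-test at each visit, gave 5.7–5.8%, 6.3% and 7.0%.

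For the Part B rule (either dose, either visit, one endpoint), the simulated null rate with everything included is 14.9% at r = 0.5 and 12.9% at r = 0.8. Taking the better of the two versions gives:

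| p | r = 0.5, separate visits | r = 0.8, separate visits | r = 0.8, borrowing across visits |
|---|---|---|---|
| 5% | 17.3% | 14.9% | 14.2% |
| 10% | 18.1% | 16.2% | 15.0% |
| 20% | 19.8% | 17.7% | 16.2% |

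At r = 0.8 with borrowing, that is about 1 to 3 points above including everything. At r = 0.5 borrowing changes little.

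**Disagreement without any selection.** With borrowing, the two versions give different overall calls in 3.9%, 6.0% and 8.8% of null trials at r = 0.5, and in 2.4%, 3.8% and 5.9% at r = 0.8.

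**The case for a change.** The strongest case for a change is that a rule defining a positive result needs a defined dataset, and that this was easy to supply. Section 9 speaks of disruption in the past tense, so the authors knew of it and could have given a criterion. Separate exploration shows the reader both sides but does not say which one is the headline. The disagreement rates above need no bad faith: an honest but unsettled choice can change the call. With a true shift of 0.3 SD in both doses (assumed), the separate-visit simulation has the versions disagreeing in about 15% to 16% of trials at a 20% share. Because analysts may be unblinded early, the order of events in Protocol 10.3 is not full protection.

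The factual part of this stands: the visible text names no primary version. What does not follow is that the plan is wrong. Some disagreement is unavoidable between any two reasonable datasets in a trial this small, and fixing one does not make it the more correct one. Late scans analysed at the nominal visit and scans dropped at a loss of precision are both defensible, and the documents give no reason to prefer either. Nor can a rule elsewhere be excluded. SAP 6.1.2 and 6.1.3.2 cite Populations A, Aa and B as defined in Section 6, but the visible section does not define them, and SAP 6.1.4 and part of Protocol 11.5 are redacted.

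**Conclusion.** The wording is loose, but no change to the plan is needed. Section 9 leaves an observation-level judgement to the team, and a competent team would resolve it in the data review before lock: list the affected scans, choose the headline version without treatment codes, and show the other alongside it. The SAP already provides for the listing and the separate examination. Both candidate analyses hold 5% per comparison when fixed in advance.

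The consequences are modest. At an assumed 20% affected share, exclusion enlarges the standard error by about 6% to 10%. Even deliberate selection would add about 1 to 5 points across the shares and correlations examined, to a Part B rule that already runs at about 13% to 15% for one endpoint by open choice. Nothing suggests such selection. These figures assume that scans are affected independently of arm and outcome, that visit correlation lies between 0.5 and 0.8, and that there are 23 completers per arm. They illustrate Part B; Section 9 itself covers both parts.
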